5.7 Treatment Compliance

5.7.1 Drug Dispensing and Accountability

Any IMP provided to the site will be accounted for. This includes IMP received at the site and IMP dispensed to subjects. A Drug Inventory and Dispensing Log will be kept current by the unblinded staff, detailing the dates and quantities of IMP received and dispensed to each subject and the remaining quantity.

The inventory and dispensing log will be available to the unblinded monitor to verify drug accountability during the study.

Unused IMP can be destroyed at the study site or returned to the Sponsor depot for destruction. Destruction can be initiated only after accountability has been verified and fully reconciled by the unblinded monitor and after the Sponsor has granted written approval of destruction. IMP that was already used for preparation of the infusion can be destroyed after preparation.

5.7.2 Assessment of Treatment Compliance

All subjects will be infused at the study site under the surveillance of authorized study personnel. Infusion details will be documented together with the batch number(s) in the source data and eCRF.

6 STUDY CONDUCT

The flow chart of assessments by study visit is given in Table 1. Details regarding each assessment are provided in Section 7.

6.1 Observations by Visit

It is anticipated that all study visits will occur while subjects are hospitalized. If a subject is discharged from the hospital prior to the End of Study Visit (Day 33), final safety blood samples (see Section 7.3.4) will be taken on day of discharge, and study data for follow-up visits thereafter will be collected by telephone or telehealth (see Section 6.1.6).

6.1.1 Screening Visit

The following assessments will be performed during the Screening Visit, which should take place within 24 hours (1 day) before the first administration of IMP, unless otherwise indicated:

1. Obtaining voluntarily given, written (signed and dated) informed consent prior to any Screening procedures being performed. Consent can be given by legally authorized representative (LAR) if subject is not able to give consent.
2. Inclusion and exclusion criteria and diagnosis confirmation (including swab for RT-PCR confirmation of SARS-CoV-2 infection or review of results from swab performed during the 7 days prior to Screening)
3. Demographic, baseline characteristics, and medical history (including COVID-19 diagnosis date (see Section 7.1.4) and infection symptoms)
4. Body weight
5. Prior medication use
6. Vital signs including SpO₂ saturation (see Section 7.2.4) or arterial blood gas to confirm eligibility
7. MQoL-SIS
8. Physical examination
Note: may be extracted from hospital admission information
9. Clinical Status and Oxygenation/Ventilator Status Evaluation
10. Blood sampling for clinical laboratory evaluations (specified in Section 7.3.4)
Note: clinical laboratory samples taken within 7 days before Screening may be used for Screening assessments
11. Serum pregnancy test for females of child-bearing potential

12. Urine sample for legionella and pneumococcal antigens
13. Chest CT/Chest X-ray

Note: may be performed within \pm 1 day of Screening Visit

6.1.2 Baseline/Infusion, Visits 1 to 4 (Day 1 to Day 4)

After screening and confirmation of eligibility, subjects will be randomized to receive either placebo or Octagam 10% (blinded). Administration of the first infusion must be started within 1 day (24 hours) after the screening visit. In this acute disease setting, the clinical status of patients can change rapidly. If a patient's eligibility status changes (eg, they require intubation and mechanical ventilation or meet other exclusion criteria) between initial confirmation of eligibility and randomization, they will not be randomized and will be considered a screening failure.

The first infusion of IMP should be initiated as soon as possible after randomization. Eligibility will not be re-assessed again between randomization and dosing. All randomized patients will therefore be dosed irrespective of changes in their clinical condition between randomization and dosing unless the Investigator decides that administration of the IMP would place the patient at additional risk.

The following activities/assessments will be performed **before** the IMP infusion on Day 1:

1. Confirmation of inclusion and exclusion criteria
2. Body weight (if not performed at Screening)
3. Vital signs
4. Physical Examination (if not performed at Screening or available from hospital admission notes, see Section 6.1.1)
5. Confirm medical history
6. Chest CT/Chest X-ray (at Day 1 if not available at Screening, see Section 7.3.6)
7. A-a Gradient (see Section 7.2.4)
8. Clinical Status and Oxygenation/Ventilator Status Evaluation
9. Blood sampling for clinical laboratory evaluations (specified in Section 7.3.4)
10. Randomization

The following activities/assessments will be performed **before** the IMP infusion on Days 2 through 4:

- Vital signs

- Clinical Status and Oxygenation/Ventilator Status Evaluation
- Blood sampling for clinical laboratory evaluations (specified in Section 7.3.4)

All blood sampling (Section 7.3.4) will be done **before** IMP infusion on all dosing days. If the Day 1 infusion commences within 8 hours of the blood collection for the Screening laboratory parameters, only those parameters not assessed at Screening need to be performed prior to the Day 1 infusion. Physical examination and body weight will be performed at Baseline (Day 1) only if it is not performed at Screening.

During and after IMP administration (Day 1 through Day 4):

The subject will receive either *Octagam 10%* medication in the dose of 2 g/kg administered over 4 days (0.5 g/kg/day), or an equivalent volume of placebo (saline), infused slowly over approximately 2 hours per day over 4 consecutive days. Note: Subjects must be monitored before infusion and carefully observed for any symptoms at least once throughout the infusion period and at least 1 hour thereafter.

The following activities/assessments will be performed on **Day 1 through Day 4**:

1. Infusion of IMP according to randomization code: *Octagam 10%* or placebo
2. Vital signs (taken once during and again after infusion)
3. SpO₂ saturation (see Section 7.2.4)
4. Post-infusion site assessment
5. Modified Borg Dyspnea Scale
6. MQoL-SIS
7. AE monitoring
8. Concomitant medication use review and documentation

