3.1.3 Exploratory Endpoints

- Improvement of SpO₂ on room air from Baseline (Day 1) to Day 33 using trend from all available observed data.
- Modified Borg Dyspnea Scale score at Baseline (Day 1) and on Days 7, 14, 21, and 33.
- MQoL-SIS score at Baseline (Day 1) and on Days 7, 14, 21, and 33.

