#### **4. General Analytic Considerations**

Unless otherwise mentioned:

- Number of subjects in the defined population and number of subjects with available data will be provided.
- Continuous variables will be summarized using descriptive statistics such as mean, standard deviation, median, quartiles, minimum, and maximum, and 95% confidence interval.
- Categorical variables (e.g., gender, race, etc.) will be provided using frequency tabulations.
- Individual listings will be provided to support the descriptive analyses.
- Baseline is defined as the last observation prior to randomization for the analysis of efficacy endpoints. Baseline is defined as the last observation prior to first administration of study drug for the analysis of safety endpoints.

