## 15. Analysis of Exploratory Endpoints

The analysis will be based on the ITT Population corresponding to each outcome. Missing data will not be imputed and endpoints will not be tested statistically. Endpoints will be presented descriptively by treatment arm.

- **Oxygen saturation on room air**

The associated endpoint is “trend of improvement of SpO2 on room air from Baseline (Day 1) to Day 33.” A side-by-side box plot of SpO2 level by treatment group will be provided.

- **Modified Borg Dyspnea Scale Score at Baseline (Day 1) and on Days 7, 14, 21, and 33**

The associated endpoints are “changes in modified Borg Dyspnea Scale from baseline (Day 1) to Days 7, 14, 21 and 33.” Descriptive statistics for crude value and absolute changes from baseline (e.g. Day 7 measurement minus baseline measurement) by treatment arm and overall will be provided for the ITT Population. Moreover, descriptive statistics for difference in change from baseline between the treatment arms will be provided for each time point. Descriptive statistics, least squares means, standard errors, and 95% CIs for mean differences will be presented. Least squares estimates presented at each visit will be based on ANCOVA models with baseline value and age category as covariates.

- **MQoL-SIS score at Baseline (Day 1) and on Days 7, 14, 21 and 33**

The associated endpoints are “changes in MQoL-SIS score from baseline (Day 1) to Days 7, 14, 21 and 33.” Descriptive statistics for crude value and absolute changes from baseline (e.g. Day 7 measurement minus baseline measurement) by treatment arm and overall will be provided for the ITT Population. Moreover, descriptive statistics for difference in change from baseline between the treatment arms will be provided for each time point. Descriptive statistics, least squares means, standard errors, and 95% CIs

for mean differences will be presented. Least squares estimates presented at each visit will be based on ANCOVA models with baseline value and age category as covariates.

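### As scheduled, the Day 1 Borg dyspnea score that serves as baseline falls after randomization and during or after the first infusion; for MQoL-SIS the plan is only unclear about which score is baseline

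*Protocol*

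**What the plan says.** - **Endpoint.** Protocol section 3.1.3 defines the exploratory endpoint as "Modified Borg Dyspnea Scale score at Baseline (Day 1) and on Days 7, 14, 21, and 33". MQoL-SIS is defined in the same way.
- **Screening.** The list in section 6.1.1 and Table 1 include MQoL-SIS at Screening. Neither includes the Borg scale.
- **Day 1 before dosing.** Under "The following activities/assessments will be performed before the IMP infusion on Day 1", section 6.1.2 lists ten activities, of which the last is "10. Randomization". Neither scale is among them.
- **Day 1 from dosing on.** Under the heading "During and after IMP administration (Day 1 through Day 4", the first item is the infusion, the fourth the post-infusion site assessment, and then comes "5. Modified Borg Dyspnea Scale". MQoL-SIS follows as item 6.
- **Assessment sections.** Section 7.2.4 requires SpO₂ on Days 1 to 4 to be taken before infusion and makes the pre-infusion Day 1 value the baseline. Sections 7.2.5 (Borg) and 7.2.6 (MQoL-SIS) contain no timing rule.
- **SAP baseline.** SAP section 4: "Baseline is defined as the last observation prior to randomization for the analysis of efficacy endpoints". This is a default that applies unless the SAP says otherwise.
- **SAP same-day rule.** Section 4.6, which names both scales, takes the latest value of a study day in the treatment period.
- **SAP analysis.** Section 15 describes change from baseline (Day 1) for both scales and adds: "Least squares estimates presented at each visit will be based on ANCOVA models with baseline value and age category as covariates". It also says that exploratory endpoints are neither imputed nor tested.

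**The concern.** A baseline used to form change scores or to adjust an ANCOVA should be unaffected by treatment. The Borg item asks about breathing at the moment of asking, so it matters whether it is asked before, during or after an infusion of about two hours. If IVIG itself changes breathlessness within that time, for better or through an infusion reaction, the change sits in the IVIG arm's baseline and not in the placebo arm's. Subtracting or adjusting for that baseline then removes part of a real effect, or adds to it.

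The rest of the plan is more careful. The primary endpoint's baseline is stated to be Day 1 before infusion, and SpO₂ has its own rule. The Borg scale has neither.

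**Working it through.** The plan states no figure on this point, so the check is one of order and definition, followed by an illustration of scale.

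**Step 1: does any scheduled score meet the SAP section 4 default?**

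| Occasion | Before randomization? | Borg | MQoL-SIS |
|---|---|---|---|
| Screening (6.1.1, Table 1) | Yes | Not scheduled | Scheduled |
| Day 1 pre-infusion list (6.1.2) | Yes, up to item 10 | Not listed | Not listed |
| Day 1 list for during and after dosing (6.1.2) | No | Item 5 | Item 6 |

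No scheduled Borg score meets the default. MQoL-SIS has one that does, the Screening score.

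**Step 2: which score does SAP section 15 then use?** It names Day 1. For Borg that is the post-randomization score. If a site records two Day 1 scores, section 4.6 selects the later one, so an extra pre-infusion score would not be used. For MQoL-SIS, section 15 points to Day 1 and section 4 to Screening, or to any later score that precedes randomization.

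**Step 3: how large could the distortion be?** Let τ be the true between-arm effect at Day 7, f the fraction of τ already present in the Day 1 score, and b the within-arm slope of the Day 7 score on baseline.

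- Change-score difference: τ − fτ = (1 − f)τ
- ANCOVA estimate: τ − b·fτ = (1 − bf)τ

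The documents give neither f nor b. The values below are assumptions that show the range.

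| f | Change score, share of τ | ANCOVA, b = 0.3 | ANCOVA, b = 0.7 |
|---|---|---|---|
| 0 | 100% | 100% | 100% |
| 0.10 | 90% | 97% | 93% |
| 0.25 | 75% | 92.5% | 82.5% |
| 0.50 | 50% | 85% | 65% |

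For example, at f = 0.25 and b = 0.7 the ANCOVA share is 1 − 0.7 × 0.25 = 0.825. A simulation at b = 0.5 gave ANCOVA shares of 87.5% (f = 0.25) and 74.6% (f = 0.50), against 87.5% and 75% from the formula.

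An early infusion reaction makes f negative and inflates the estimate. At f = −0.10 the change score gives 1 + 0.10 = 110% of τ, and ANCOVA gives 1 + 0.3 × 0.10 = 103% to 1 + 0.7 × 0.10 = 107%.

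**The case against.** **The second Day 1 list is not a strict clock.** SpO₂ is item 3 on it and is nevertheless taken before infusion. This stands in part: a site could ask the Borg item before dosing without breaking the protocol. But SpO₂ is pre-infusion only because section 7.2.4 says so, and nothing says so for Borg. The list also follows randomization either way.

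**The change can be computed.** A reader might infer from SAP section 4 that no Borg baseline exists and that the change is undefined for everyone. The documents do not support that. Section 4 is a default, and section 15 can be read as overriding it by naming Day 1. The problem is the quality of that baseline.

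**Volume is matched.** A reader might also infer that the fluid load of the first infusion biases the comparison. It does not, because section 5.4 gives placebo at the same volume and rate. Only a product-specific effect can differ between arms.

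**An effect within hours may not exist.** The Introduction expects efficacy at 2 to 10 days, and the fastest improvement timed in section 1.1 is 24 to 48 hours. This stands for benefit. Infusion reactions, which section 1.2 links to dose and rate, remain possible on Day 1.

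**MQoL-SIS does not share the defect.** Besides its Screening score, its two-day recall means that even a post-infusion Day 1 answer mostly covers time before dosing. This stands.

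**Table 1 footnotes.** The Day 1 column carries a footnote whose text I did not have. The Borg and MQoL-SIS rows carry no footnote mark, but a timing note for the visit cannot be excluded.

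**Conclusion.** The Borg point holds. Followed as written, the plan produces a Borg baseline that is post-randomization and taken during or after the first infusion, in conflict with the SAP's default definition. It reaches every Borg change score and ANCOVA estimate at Days 7, 14, 21 and 33.

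The direction and size of any bias are unknown. It is zero if IVIG has no product-specific effect on dyspnea within hours of the first dose, and the percentages above are illustrations only. For MQoL-SIS the finding is a mismatch between the Day 1 label and the SAP default, with a valid Screening score available.

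Both endpoints are exploratory and untested, so no primary or key secondary conclusion depends on this. The verdict assumes that no Table 1 footnote sets a pre-infusion time for the Borg scale.

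**What to change.** **Protocol.** In section 6.1.2, move the Day 1 Borg and Day 1 MQoL-SIS to the pre-infusion list, ahead of randomization. Add a Day 1 pre-infusion rule to sections 7.2.5 and 7.2.6. Days 2 to 4 need no change, because neither endpoint uses them.

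**SAP section 15.** Name the baseline for each scale, with an exception to the latest-value rule in section 4.6:

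- Borg: the Day 1 pre-infusion score.
- MQoL-SIS: the last score before randomization, which is the Screening score if no Day 1 score precedes randomization.

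**Subjects already enrolled.** SAP section 8 describes a data review at 50% enrollment as already past, so reordering the visit cannot repair those records. Use a Day 1 Borg score as baseline only if it is timed before the start of infusion. Otherwise, compare observed Borg scores at Days 7, 14, 21 and 33 between arms without baseline adjustment. This needs a recorded time for the Day 1 score; a score without one should not qualify.

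**Cost.** No extra instrument or visit: two short items already collected that day move earlier, and the SAP gains a few sentences. The downside is that some enrolled subjects may have no qualifying Borg baseline and would drop out of the change-from-baseline analysis, and the unadjusted comparison that replaces it may be less precise.

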6.1.3 Endpoint Visit 5 (Day 7)

The following assessments will be performed 3 days after the end of daily infusions (Day 7 or on day of discharge if prior to Day 6 and restrictions prevent inpatient Day 7 visit and not already performed as part of the assessments for that day):

1. Vital signs
2. SpO₂ saturation and A-a Gradient (see Section 7.2.4) (for subjects discharged prior to Day 6, telephone contact will be made with the subject on Day 7 to ascertain SpO₂)
3. Swab for RT-PCR detection of SARS-CoV-2 to determine infection status
4. Clinical Status and Oxygenation/Ventilator Status Evaluation

5. Modified Borg Dyspnea Scale
6. MQoL-SIS
7. Chest CT/Chest X-ray
8. Blood sampling for clinical laboratory evaluations (specified in Section 7.3.4)
9. AE monitoring
10. Concomitant medication use

6.1.4 Follow-up Visits 6 and 7 (Day 14 and Day 21)

The following safety assessments will be performed at Day 14 and Day 21 (see Section 6.1.6. if subject has been discharged):

1. Vital signs
2. SpO₂ saturation (see Section 7.2.4)
3. Clinical Status and Oxygenation/Ventilator Status Evaluation
4. Modified Borg Dyspnea Scale
5. MQoL-SIS
6. AE monitoring
7. Concomitant medication use

6.1.5 End of Study (Final Examination) Visit (Day 33)

An End of Study Visit will be performed and include the following assessments (see Section 6.1.6 if subject has been discharged):

1. Vital signs
2. Physical examination
 - Note:** may be extracted from daily physical examinations in hospital chart
3. SpO₂ saturation (see Section 7.2.4)
4. Clinical Status and Oxygenation/Ventilator Status Evaluation
5. Modified Borg Dyspnea Scale
6. MQoL-SIS
7. Blood sampling for clinical laboratory evaluations (specified in Section 7.3.4)
8. AE monitoring
9. Concomitant medication use

After Day 33, the core clinical study is considered completed for the subject. No further study-related assessments will be performed, unless safety concerns (eg, ongoing AEs) require follow-up. After completion of the core 33-day trial, all subjects will be followed for a one-year follow-up registry. Subjects will be contacted by telephone or electronically by the Principal Investigator or the Sponsor (or its designee) every three months (± 14 days) for one year to obtain data on health status and any residual health effects from COVID-19 or the study treatment. There will not be any additional in-person site visits required. The responsibility for the oversight of this registry follow-up period will be managed by a central Coordinating Principal Investigator (not the enrolling Investigator responsible for the 33-day core trial), unless the local Investigator elects to continue to oversee their subjects directly during this one-year follow-up period. The data recorded during this registry follow-up period will be submitted as a supplement to the core study data once all subjects have completed one year of follow-up.

6.1.6 Telephone Visits

If a subject is discharged from the hospital at any time during the course of their participation in the study, a pulse oximeter will be provided to them to monitor their oxygen saturation at home. The Research Coordinator or other qualified research team member will contact the subject on Day 7 (if discharge took place on Day 5 or earlier), Day 14, Day 21, and Day 33 (if discharge took place prior to Day 33) at approximately the same time (± 2 hours) as the pre-infusion SpO₂ measurement recorded at Baseline (Day 1), to collect the following data points:

1. Clinical Status
2. SpO₂ saturation taken on resting room-air
3. AE and Concomitant medication review
4. Modified Borg Dyspnea Scale
5. MQoL-SIS

6.1.7 Subject Early Discontinuation

A study subject has a right to refuse study treatment and study visits at any time and for any reason. A subject can also withdraw from the study or study drug treatment for AEs, in which case the subject will be followed until resolution of the AE. Every effort will be made to assess the effect and outcome of the AE.

6.1.8 Time Windows Used in this Study, Including Tolerances

In this study, the following time windows and tolerances apply:

Table 2: Time Windows Used in this Study

Time point	Time stated	Tolerance
Screening Visit	24 hours before Visit 1	Max of 26 hours
Visits 1 to 4	Day 1 to 4	None
Visit 5	Day 7 or discharge day	± 1 day
Visit 6 and 7	Days 14 and 21	± 2 days
End of Study Visit	Day 33	± 3 days
Q3 month post-study follow-up	Every 3 months after completion of core trial or early termination	± 14 days

6.2 Duration of Study

6.2.1 Planned Duration for an Individual Subject

The duration of the core study for each subject will be approximately 33 days: 1 day for Screening, 4 days for the treatment, and 29 days for safety follow-up and end of study assessments. Subsequently, subjects will be followed remotely for an additional year to record any new COVID-19 safety developments.

6.2.2 Planned Duration for the Study as a Whole

The study will be considered completed when all subjects have completed the planned observation period/End of Study Visit.

The estimated start of the study (enrollment of first subject) is Q2 2020 and the estimated end of the study (last visit of last subject) is Q4 2020.

6.2.3 Premature Termination of the Study

Both the Investigator and the Sponsor reserve the right to terminate the study at any time. In this event, any necessary procedures will be arranged on an individual study basis after review and consultation by both parties. In terminating the study, the Sponsor and the Investigators will ensure that adequate consideration is given to the protection of the subjects' interests.

Regulatory authorities and Independent Ethics Committee (IEC)/Institutional Review Board (IRB) should be informed in accordance with national regulations.

Early termination of the study as a whole or by center may apply for the following reasons:

6.2.3.1 Early Termination of the Entire Clinical Study

At any time, the study as a whole will be terminated prematurely if:

- New toxicological or pharmacological findings or safety reports invalidate the earlier positive benefit-risk-assessment.
- Any other reason rendering the continuation of the study impossible for the Sponsor.

